12. STATISTICS

12.1. Analysis Populations

12.1.1. Randomized Population

The randomized population will include all patients who sign the informed consent form and are assigned a randomization number at Visit 2 (Day 0).

12.1.2. Intent-to-Treat Population

The Intent-to-Treat (ITT) population will consist of all randomized patients who take at least one dose of study drug. The ITT population is the primary analysis population. All efficacy analyses will be performed on the ITT population.

12.1.3. Per-Protocol Population

The per-protocol (PP) population will include all ITT patients without any major protocol deviations, and who had $\geq 80\%$ compliance with study drug while on treatment (up to discontinuation for patients whose treatment is terminated early). The per-protocol efficacy analysis for CV events will be restricted to each patient's time on study drug plus 30 days thereafter.

12.1.4. Safety Population

All safety analyses will be conducted based on the safety population, which is defined as all randomized patients who receive at least one dose of study drug. This is the same as the ITT population.

12.2. Statistical Methods

Safety and efficacy variables will be analyzed using appropriate statistical methods to be described in detail in a separate Statistical Analysis Plan (SAP). The SAP will be finalized before study unblinding.

12.2.1. Patient Disposition and Demographic/Baseline Characteristics

The numbers of patients screened, the number of patients randomized per treatment group (randomized population), and the number of patients in the ITT and PP populations by treatment group will be listed.

For randomized patients who discontinued treatment with study drug, the primary reason for discontinuation will be listed and summarized by treatment group.

Summary statistics (mean, standard deviation, median, minimum and maximum) will be provided by treatment group for demographic characteristics (e.g., age, sex, race, and ethnicity) and baseline characteristics (e.g., body weight, height, and body mass index) in the ITT and PP populations.

Demographic data and baseline characteristics will be compared among treatment groups for the ITT and PP population. Differences in demographic and baseline characteristics will be tested using a chi-square test (for categorical variables) or a 1-way analysis of variance model with treatment as a factor (for continuous variables). The p-values will be used as descriptive statistics, primarily as an assessment of the adequacy of randomization.

12.2.2. Study Medication Exposure and Compliance

The final compliance to study drug will be calculated as the percent of doses taken relative to doses scheduled to be taken. Overall percent compliance will be calculated per patient in the ITT and PP populations and summarized by treatment group using summary statistics (n, mean, standard deviation, median, minimum, and maximum).

12.2.3. Concomitant Therapies

Concomitant medication/therapy verbatim terms will be coded using the latest version of the World Health Organization Drug Dictionary. The numbers and percentages of patients in each treatment group taking concomitant medications will be summarized by anatomic and therapeutic chemical classification and preferred term.

12.2.4. Analysis of Efficacy

For efficacy endpoints including CV events, only adjudicated events will be included in the final statistical analyses.

12.2.4.1. Summary Statistics

Summary statistics (n, mean, standard deviation, median, minimum, and maximum) for the baseline and post-baseline measurements, the percent changes, or changes from baseline will be presented by treatment group and by visit for all efficacy variables to be analyzed. The summary statistics will include changes in body weight and body mass index from baseline by treatment group and by visit.

12.2.4.2. Primary Endpoint

The primary efficacy endpoint is the time from randomization to the first occurrence of any component of the composite of the following clinical events:

- CV death,
- Nonfatal MI (including silent MI),
- Nonfatal stroke,
- Coronary revascularization,
- Hospitalization for unstable angina determined to be caused by myocardial ischemia by invasive/non-invasive testing.

The analysis of the primary efficacy endpoint will be performed using the log-rank test comparing the 2 treatment groups (AMR101 and placebo) and including the stratification factor “CV risk category”, use of ezetimibe and geographical region (Westernized, Eastern European, and Asia Pacific countries) (each as recorded in the IWR at the time of

enrollment) as covariates. Treatment difference will be tested at alpha level of 0.0476 accounting for one interim efficacy analysis. The hazard ratio for treatment group (AMR101 vs. placebo) from a Cox proportional hazard model that includes the stratification factor will also be reported, along with the associated 95% confidence interval. Kaplan-Meier estimates from randomization to the time to the primary efficacy endpoint will be plotted.

The size and direction of the treatment effects of the individual components of the composite endpoint and their relative contribution to the composite endpoint will be determined as well.

12.2.4.3. Secondary Endpoints

The statistical analyses of the secondary endpoints will be analyzed by the same log-rank test specified above for the primary efficacy endpoint. Treatment differences will be tested at alpha level of 0.05 using a sequential procedure for controlling type 1 error starting with the key secondary variable. The remaining secondary variables will be tested in the order specified in Section 9.2.2. Estimates of the hazard ratios from the Cox proportional hazard model and the associated 95% confidence intervals will also be provided. Kaplan-Meier estimates from randomization the time to the secondary efficacy endpoints will be plotted.

12.2.4.4. Tertiary Endpoints

For event rates, the statistical analyses of the tertiary endpoints (see section 9.2.3) will be similar to the analysis of the secondary efficacy endpoints. All tertiary analyses will be conducted for the ITT population. No adjustments for multiple testing will be made.

For measurements of lipids, lipoproteins and inflammatory markers the change from baseline will be analyzed in the units of each marker, and the percent change from baseline. Since these biomarkers are typically not normally distributed, the Wilcoxon rank-sum test will be used for treatment comparisons of the percent change from baseline, and medians and quartiles will be provided for each treatment group. The medians of the differences between the treatment groups and 95% confidence intervals will be estimated with the Hodges-Lehmann method.

New onset diabetes is defined as Type 2 diabetes newly diagnosed during the treatment/follow-up period (i.e. patients with no history of diabetes at randomization, with the test as listed in Appendix C).

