6.1.1. Screening Period

6.1.1.1. Screening Visit (Visit 1)

Patients will come to the Research Site for Visit 1. They will be instructed to fast for at least 10 hours before their visit.

If patients qualify for randomization based on the procedures at Visit 1, they need to be randomized within 42 days after Visit 1. The following procedures will be performed at the screening visit:

- Obtain signed informed consent
- Assign the patient a patient number
- Obtain medical, surgical and family history
- Record demographics
- Obtain height, weight, and body mass index
- Obtain vital signs (systolic and diastolic blood pressure, heart rate, respiratory rate, and body temperature)
- Obtain a 12-lead electrocardiogram
- Evaluate inclusion/exclusion criteria
- This includes procedures and (fasting) blood samples (for example, hs-CRP, calculated creatinine clearance) as needed to determine the CV risk category (see inclusion criteria)
- Obtain fasting blood samples for chemistry and hematology testing
- Obtain a fasting blood sample for the lipid profile (TG, TC, HDL-C, LDL-C, non-HDL-C, VLDL-C)

- Perform a urine pregnancy test on women of childbearing potential
- Record concomitant medication(s)
- Instruct patient to fast for ≥ 10 hours prior to the next visit

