6.1.2.1. Randomization visit (Visit 2; Day 0)

Qualified patients will return to the Research Site for Visit 2.

The following procedures will be performed at Visit 2:

- Perform physical examination
- Obtain weight
- Obtain vital signs (systolic and diastolic blood pressure, heart rate, respiratory rate, and body temperature)
- Measure waist circumference (one of the factors to diagnose metabolic syndrome)
- Obtain a 12-lead electrocardiogram
- Evaluate inclusion/exclusion criteria
- Obtain fasting blood samples for:
 - Chemistry and hematology testing
 - Lipid profile (baseline)
 - Biomarker assays (baseline)
 - Genetic testing (optional blood sample)
 - Archiving (in countries and at sites approved by IRB/IEC and dependent on country regulations)
- Perform a urine pregnancy test on women of childbearing potential (must be negative for randomization)
- Dispense study drug and record randomization number
- Instruct patient on how to take study drug
- Administer study drug - Note: Study drug should be taken orally with food following the collection of all fasting blood samples
- Assess for and record adverse events
- Record concomitant medication(s)
- Instruct patient:
 - To bring all study supplies with them to the next visit
 - Not to take study drug on the morning of their next visit
 - To fast for ≥ 10 hours prior to the next visit

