6.1.2.2. Visit 3 (Day 120; ~4 Months)

Patients will return to the Research Site for Visit 3 on Day 120 ± 10 days.

The following procedures will be performed:

- Perform physical examination
- Obtain weight
- Obtain vital signs (systolic and diastolic blood pressure, heart rate, respiratory rate, and body temperature)
- Obtain fasting blood samples for:
 - Chemistry and hematology testing
 - Lipid profile
- Review study drug compliance by unused capsule count; discuss with and counsel patients about compliance if needed
- Administer study drug - Note: Study drug should be taken orally with food following the collection of all fasting blood samples
- Assess and record efficacy events
- Assess for and record adverse events
- Record concomitant medication(s)
- Instruct patient:
 - To bring all study supplies with them to the next visit
 - Not to take study drug on the morning of their next visit
 - To fast for ≥ 10 hours prior to the next visit

6.1.2.3. Visits 4, 5, 6 and 7

At Visit 4: Day 360 ± 10 ; Visit 5: Day 720 ± 10 ; Visit 6: Day 1080 ± 10 ; and Visit 7: Day 1440 ± 10 , the following procedures will be performed:

- Perform physical examination
- Obtain weight
- Obtain vital signs (systolic and diastolic blood pressure, heart rate, respiratory rate, and body temperature)
- Measure waist circumference (collected at Visit 5 only)
- Obtain a 12-lead electrocardiogram
- Obtain fasting blood samples for:
 - Chemistry and hematology testing
 - Lipid profile
 - Biomarker assays (collected at Visit 5 only)
 - Archiving (in countries and at sites approved by IRB/IEC and dependent on country regulations)

- Review study drug compliance by unused capsule count; discuss with and counsel patients about compliance if needed
- Administer study drug - Note: Study drug should be taken orally with food following the collection of all fasting blood samples
- Assess and record efficacy events
- Assess for and record adverse events
- Record concomitant medication(s)
- Instruct patient:
 - To bring all study supplies with them to the next visit
 - Not to take study drug on the morning of their next visit
 - To fast for ≥ 10 hours prior to the next visit

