6.3.1.1. Safety Laboratory Tests

The safety laboratory tests include:

- Hematology with complete blood count (CBC), including RBC, hemoglobin (Hgb), hematocrit (Hct), white cell blood count (WBC), white cell differential, and platelet count
- Biochemistry panel including total protein, albumin, alkaline phosphatase, alanine aminotransferase (ALT/SGPT), aspartate aminotransferase (AST/SGOT), total

bilirubin, glucose, calcium, electrolytes (sodium, potassium, chloride), blood urea nitrogen (BUN), serum creatinine, uric acid, creatine kinase, and HbA_{1c}.

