9. Safety Laboratories — Complete Blood Count: Includes RBC, Hgb, Hct, WBC and differential, and platelet count. Biochemistry includes total protein, albumin, alkaline phosphatase, ALT, AST, total bilirubin, glucose, calcium, electrolytes (sodium, potassium, chloride), blood urea nitrogen (BUN), serum creatinine, uric acid, creatine kinase, HbA1c. Safety labs may be repeated as deemed necessary by the Investigator.
10. TG, TC, HDL-C, LDL-C, non-HDL-C, and VLDL-C.
11. Fasting blood sample that will be stored for future genetic testing at the discretion of the sponsor. This sample is optional as local regulations may prohibit genetic samples to be collected or shipped outside the country, or patients may not consent.
12. Used at the sponsor's discretion to perform repeat analyses described in the protocol or to perform other tests related to cardiovascular health.
13. Site personnel will contact each patient by telephone in-between Visit 2 and Visit 3 and between Visit 3 and Visit 4. After Visit 4 contact will be made every 3 months. The purpose of the contact is to collect information about efficacy events, adverse events, concomitant medications, confirm patient's current address and contact information and remind patients about taking their study medication and logistics for the next visit.
14. The last visit (LV) may occur within 30 day after the study end date as determined by the DMC; the study end date is tentatively schedule for Day 1800 but the actual date as determined by the DMC may be different.

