APPENDIX C: CRITERIA FOR THE DIAGNOSIS OF DIABETES

Reference:

American Diabetes Association. Diagnosis and classification of diabetes mellitus. Diabetes Care 2010; 33 Suppl 1:S62.

1. HbA_{1c} \geq 6.5%. The test should be performed in a laboratory using a method that is National Glycohemoglobin Standardization Program (NGSP) certified and standardized to the Diabetes Control and Complications Trial (DCCT) assay.*

OR

2. Fasting plasma glucose (FPG) \geq 126 mg/dL (7.0 mmol/L). Fasting is defined as no caloric intake for at least 8 hr.*

OR

3. 2-hr plasma glucose \geq 200 mg/dL (11.1 mmol/L) during an Oral Glucose Tolerance Test (OGTT). The test should be performed as described by the World Health Organization, using a glucose load containing the equivalent of 75 g anhydrous glucose dissolved in water.*

OR

4. In a patient with classic symptoms of hyperglycemia or hyperglycemic crisis, a random plasma glucose \geq 200 mg/dL (11.1 mmol/L).

* In the absence of unequivocal hyperglycemia, criteria 1–3 should be confirmed by repeat testing.

CLINICAL STUDY PROTOCOL

A Multi-Center, Prospective, Randomized, Double-Blind,
Placebo-Controlled, Parallel-Group Study to Evaluate the Effect of AMR101
on Cardiovascular Health and Mortality in Hypertriglyceridemic Patients
with Cardiovascular Disease or at High Risk for Cardiovascular Disease:
REDUCE-IT (Reduction of Cardiovascular Events with EPA – Intervention Trial)

Investigational Product: AMR101 (icosapent ethyl [ethyl-EPA])

Protocol Number: AMR-01-01-0019

Sponsor:

Amarin Pharma Inc.

[name]

[name]

[contact]

[contact]

Amendment #2: Final 8 July 2016

Amendment #2 Protocol Version Number: Final v 3.0

Amendment #1: Final 16 May 2013

Amendment #1 Protocol Version Number: Final v 2.0

Original Protocol: 2 August 2011

Confidentiality Statement

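### New-onset diabetes: with the risk set defined by history alone, undiagnosed diabetes present at baseline can be counted as incident, which dilutes the hazard ratio toward 1

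*Combined protocol and SAP*

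**What the plan says.** Section 12.2.4.4 of Amendment 1 gives the definition: "New onset diabetes is defined as Type 2 diabetes newly diagnosed during the treatment/follow-up period", with the at-risk patients described as "patients with no history of diabetes at randomization, with the test as listed in Appendix C". The 2011 protocol has the same rule in the same section. Section 9.2.3 lists the endpoint among the tertiary efficacy endpoints. Section 12.2.4.4 analyses tertiary event endpoints like the secondary ones, by log-rank test and Cox hazard ratio, without multiplicity adjustment.

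Appendix C sets the diagnostic criteria, including HbA1c of at least 6.5% and fasting plasma glucose of at least 126 mg/dL. Its footnote adds that, absent unequivocal hyperglycemia, "criteria 1–3 should be confirmed by repeat testing".

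The relevant tests are already in the schedule. At Visit 1 (Section 6.1.1.1) sites are to "Obtain fasting blood samples for chemistry and hematology testing", and the fasting samples at Visit 2 (Section 6.1.2.1) again include "Chemistry and hematology testing". The panel contains glucose and, in Appendix A footnote 9, "serum creatinine, uric acid, creatine kinase, HbA1c". It is repeated from Visit 3 (Day 120) onward. The only glycemic exclusion is HbA1c above 10.0% (Section 4.2, criterion 4).

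**The concern.** The two halves of the definition use different yardsticks. A patient in CV Risk Category 1 can enter with vascular disease, no recorded diabetes, and an HbA1c anywhere from 6.5% to 10.0%. Nothing in the reviewed text removes that patient from the risk set. If diabetes is then established during follow-up, the patient can be counted as a new case although the condition preceded randomization.

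Randomization balances such patients in expectation, so they add a similar number of cases to each arm and carry no information about the drug. A relative measure is pulled toward 1. That matters most if the result is read as reassurance that the drug does not cause diabetes, but a true benefit would be blunted in the same way.

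**Working it through.** **No figure to reproduce.** The documents give no incidence, effect size or power for new-onset diabetes. The rates below are assumptions chosen to show a range.

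**Can prevalent cases enter?** Category 2 patients all have medically treated diabetes (Section 4.1), so the risk set lies within Category 1. That is about 70% of patients (Section 3.10), or 0.70 × 3995 ≈ 2797 per arm before known diabetics are removed. Category 1 entry needs no diabetes work-up. The history is the medical history described in Section 6.3.2.1. The event committee's remit in Section 5.3 is primary and secondary events, so no adjudication step is described that would strip prevalent cases from this tertiary endpoint.

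**Inputs (assumed).** u = undiagnosed share of history-negative patients, 3% to 8%. I = true 4-year incidence in control patients without diabetes, 6% to 10%. d = proportion of prevalent cases detected, confirmed and counted, 0.7 to 1.0, equal in both arms. True risk ratio RR = 1.30. The risk ratio stands in for the hazard ratio.

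**Formulas.**
- Observed RR = [u·d + (1−u)·I·RR] / [u·d + (1−u)·I]
- Prevalent share of control cases s = u·d / [u·d + (1−u)·I]
- Equivalently, observed RR = 1 + (1−s)(RR−1)

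| u | I | d | Control: prevalent + incident | Observed RR | s |
|---|---|---|---|---|---|
| 3% | 10% | 1.0 | 0.030 + 0.0970 = 0.1270 | 0.1561/0.1270 = 1.23 | 24% |
| 3% | 10% | 0.7 | 0.021 + 0.0970 = 0.1180 | 0.1471/0.1180 = 1.25 | 18% |
| 5% | 6% | 1.0 | 0.050 + 0.0570 = 0.1070 | 0.1241/0.1070 = 1.16 | 47% |
| 8% | 6% | 1.0 | 0.080 + 0.0552 = 0.1352 | 0.15176/0.1352 = 1.12 | 59% |
| 8% | 6% | 0.7 | 0.056 + 0.0552 = 0.1112 | 0.12776/0.1112 = 1.15 | 50% |

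**Benefit.** With a true RR of 0.80 and the same extreme shares (s = 17.8% and 59.2%), the observed RR is 1 − 0.822 × 0.20 = 0.84 to 1 − 0.408 × 0.20 = 0.92.

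**Absolute scale.** The risk difference shrinks only by the factor (1−u), that is 0.97 to 0.92. For I = 6% and RR = 1.30 the true difference is 1.8 percentage points; at u = 8% it becomes 0.92 × 1.8 = 1.66. The distortion is mainly in the relative measure, which is what the plan reports.

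**Unequal detection.** If prevalent cases are detected k times as often on the drug, observed RR = s·k + (1−s)·RR. Take u = 5%, I = 10%, d = 0.7, so s = 0.035/0.130 = 0.269. With true RR = 1.25, k = 1 gives 1.18 and k = 1.4 gives 1.29. With true RR = 1.00, k = 1 gives 1.00 and k = 1.1 gives 1.03. Dilution toward 1, and the absence of a false positive, therefore both rest on similar detection by arm.

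**The case against.** Several points on the other side have force.

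- **Confirmation.** A reader might infer that a baseline-positive patient becomes an event at the first follow-up blood draw. Appendix C does not support that, because it asks for a repeat test unless hyperglycemia is unequivocal. This slows counting, but a truly prevalent case will usually repeat positive.
- **Recognition before Day 0.** The Visit 1 HbA1c must be known before randomization because an exclusion depends on it, and Section 6.3.1 has the investigator review and sign every laboratory report. A site may record diabetes as history at that stage, and the patient then leaves the risk set. Nothing requires this, so the supportable statement is that such patients can be counted, not that they are.
- **Ambiguous wording.** The mention of Appendix C inside the parenthesis could be read as describing status at randomization, which would close the gap. The more natural reading attaches it to the follow-up diagnosis. If the other meaning is intended, the text should say so.
- **Hidden harm.** A reader might infer that the rule would conceal a diabetes signal. That goes too far. Glucose and HbA1c are also safety laboratory tests, summarized by arm as change from baseline (Section 12.2.5), so a glycemic effect has a second route to view.
- **Text not seen.** The reviewed text has the Amendment 2 title page but not its body, and Section 12.2 defers detail to a separate SAP that is also absent. A later definition may already deal with this. Deferral does not change the rule as stated.

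**Conclusion.** The point stands in limited form. As written, the rule allows undiagnosed baseline diabetes to be counted as incident. If detection is similar in both arms, the hazard ratio is diluted toward 1, for harm or benefit alike. On the assumed ranges, a true risk ratio of 1.30 would appear as about 1.12 to 1.25, with about 18% to 59% of counted control cases prevalent. These figures are illustrations; the documents supply none of the rates.

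The definition does not produce a spurious difference when there is none and detection is equal, and it has no bearing on the primary endpoint. The cost is lost sensitivity on one tertiary endpoint.

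**What to change.** For the main analysis of new-onset diabetes, define the risk set as patients with no history of diabetes, no glucose-lowering drug at baseline, and baseline laboratory values that do not meet Appendix C. Use the Visit 1 and Visit 2 values together, so that exclusion follows the same repeat-confirmation rule as the event. Excluding on one unconfirmed value would apply a looser standard at baseline than afterwards and could remove near-threshold patients who are not confirmed diabetic.

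Keep two sensitivity analyses: the present history-only definition, and exclusion of anyone with a single baseline value at or above threshold.

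The cost is a short addition to the SAP and a slightly smaller risk set. At the assumed 3% to 8%, and taking all of Category 1 as an upper bound, that is at most about 0.03 × 2797 = 84 to 0.08 × 2797 = 224 patients per arm. No new measurement is needed. The sponsor should first check whether Amendment 2 or the SAP already contains an equivalent rule.
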